Determine whether there is a benefit of support as usual (SAU) plus Standard Teen Triple P (TEEN TRIPLE P) over support as usual (SAU) in improving parent/carer rated adolescent externalising behaviour problems at 6-months post-randomisation in adolescents at the edge of care.

Secondary objectives (SO):

1. Complete an Internal Pilot in the first year to inform the decision as to whether proceeding with a definitive trial is warranted and feasible.
2. Determine whether TEEN TRIPLE P + SAU, (a) reduces parent reported adolescent internalising behaviour and increases prosocial behaviours at 6 months and 12 months post-randomisation, and parent reported adolescent externalising behaviour at 12 months post-randomisation, and (b) reduces adolescent reported externalising and internalising behaviour problems and increases prosocial behaviours at 6 and 12 months post-randomisation, (c) improves parenting practices, parent self-regulation, interparental relationships, parental-adolescent relationships and parental well-being at 6 and 12 months post-randomisation, decreases adolescent reported antisocial behaviours at 12 months post-randomisation, and (d) reduces the chance of a child going into out of home placement over a 12 month period.
3. Carry out exploratory sub-group analyses of outcomes by adolescent learning disability status and whether living with foster versus biological/adoptive parents.
4. Monitor and report and adverse events related to TEEN TRIPLE P.
5. Complete a process evaluation using key indicators drawn from the logic model, including an evaluation of acceptability and the experiences of parents/carers, adolescents with a broad range of ethnic and diverse backgrounds, and other key stakeholders (e.g., practitioners, delivery team), and fidelity of delivery of TEEN TRIPLE P.

Internal pilot

The design incorporates an internal pilot in the first year with progression criteria (Avery et al., 2017) to examine whether moving on to complete a definitive trial is warranted. The proposed criteria are:

Recruitment

(i) 50% of overall final trial target (families) within first 6 months of recruitment to the trial (green=80 to 100% (n=99)); amber=60 to 79%; red=<60%);

Randomisation

(i) Proportion of recruited families randomised (green= $\geq 90\%$; amber=50-89%; red=<49%).

Fidelity and adherence (first 3-4 months of those randomised to TEEN TRIPLE P who will have completed intervention by the progression decision point)

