- (2) Parenting practices: Parenting Scale Adolescent version (PSA, parent completed) is a short form of the Parenting Scale (Irvine et al., 1999) which assesses dysfunctional discipline

practices in parents. It is an adaptation of the Parenting Scale (Arnold, et al., 1993) for parents of adolescents

(3) Adolescent prosocial behaviours – The Prosocial behaviour subscale of the SDQ (Goodman, 1999) will be used to assess adolescent prosocial behaviours. This will be completed by adolescents and parents.

(4) Adolescent peer relationships – The Peer Relationship Problem subscale of the SDQ (Goodman, 1999) will be used to assess adolescent peer relationships. This will be completed by adolescents and parents.

(5) Interparental outcome - Dyadic Adjustment Scale (DAS-7) is a 7-item measure (Sharpley & Cross 182; Hunsley et al., 2001) assessing the relationship quality of couples. The DAS-7 assesses relationship satisfaction and the degree to which the couple agrees on matters of importance to the relationship.

(6) Parent mental health – the Kessler 6 is a six-item screening tool for serious mental illness in the general population (Kessler et al., 2003). It will be completed by parents.

(7) Parent Wellbeing - The Warwick-Edinburgh Mental Well-being Scale (SWEMWBS) is a measure of mental wellbeing (Tennant et al., 2007). The short (7 item) version will be completed by parents.

(8) Conflict Behavior Questionnaire (CBQ-20) (Robin & Foster, 1989) assesses adolescent-parent communication, conflict and relations. Both the adolescent and parent report versions will be completed.

(9) Child-parent relationship – the Closeness subscale of the Child-Parent Relationship Scale (CPRS, short form) measures (Pianta, 1995) will be completed by parents.

(10) Family functioning – the Family APGAR scale (Adaptability, Partnership, Growth, Affection and Resolve; APGAR) measures satisfaction with family functioning (Smilkstein, 1978). This 5-item measure will be completed by parents.

(11) Parent self-regulation – the Parenting Self-Regulation Scale is a 12-item parent-completed measure of parental-regulation (Tellegen et al., 2022).

(12) Out of home placement – all instances of out of home placement will be recorded at each follow-up time point. This will include the reason for and duration of out of home placement.

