- A copy of the most recent approved version of the Participant Information Sheet(s) and Consent Form(s), including naming of the relevant Local Authority site
- Upon receipt of all the above documents, the Trial Manager will send written confirmation to the Principal Investigator detailing that the site is now ready to recruit participants into the trial. This letter/email must be filed in each site's Site File.

Occasionally during the trial, amendments may be made to the trial documentation listed above. The University of Warwick Trial Manager will issue the site with the latest version of the documents as soon as they become available. It is the responsibility of the University of Warwick Trial Manager to ensure that they obtain local approvals for the new documents.

Site initiation/ training will be by teleconference.

Participants

Families are eligible for the trial if they meet all the following inclusion criteria and none of the exclusion criteria apply. All queries about family eligibility should be directed to the Trial Manager before randomisation/recruitment. Figure 1 details the participant flow through the trial.

Inclusion

- Families of young people aged 11-15 years determined as being on the *edge-of-care*

Definition of *Edge-of-Care*

Edge of Care refers to children/young people who either:

- have not entered into care as they have been assessed and the LA has chosen to support them and their families through alternative provisions/services. Or
- they are being considered for care but have not entered into local authority care.

Exclusion

- Families where one or more parent has received a multi-session parenting programme covering similar content to Triple P over the previous 12-months
- Families where one or more parent is currently receiving a multi-session parenting programme covering similar content to Triple P or any multi-component manualised family intervention, such as Multi-Systemic Therapy

Sample size calculations

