Secondary outcome and data source	
(1) Strengths and Difficulties Questionnaire (SDQ; Goodman, 1999) parent report internalising problems scale, adolescent report externalising and internalising problems scales.
 
(2) Parenting practices: Parenting Scale Adolescent version (PSA) parent report
 
(3) Adolescent prosocial behaviours – The Prosocial behaviour subscale of the SDQ (Goodman, 1999). Adolescent and parent report.
 
(4) Adolescent peer relationships – The Peer Relationship Problem subscale of the SDQ (Goodman, 1999). Adolescent and parent report.
 
(5) Interparental outcome - Dyadic Adjustment Scale (DAS-7) is a 7-item measure (Sharpley & Cross 182; Hunsley et al., 2001). Parent report.
 
(6) Parent mental health – the Kessler 6 (Kessler et al., 2003). Parent report.
 
(7) Parent Wellbeing - The Warwick-Edinburgh Mental Well-being Scale (SWEMWBS; Tennant et al., 2007). Parent report.
 
(8) Conflict Behavior Questionnaire (CBQ-20) (Robin & Foster, 1989). Parent and adolescent report.
 
(9) Child-parent relationship – the Closeness subscale of the Child-Parent Relationship Scale (CPRS, short form) measures (Pianta, 1995). Parent report.
 
(10) Family functioning – the Family APGAR scale. (Adaptability, Partnership, Growth, Affection and Resolve; APGAR; Smilkstein, 1978). Parent report.

	
(11) Parent self-regulation – the Parenting Self-Regulation Scale is a 12-item parent-completed measure of parental-regulation (Tellegen et al., 2022).
 
(12) Antisocial behaviours - Self Report Delinquency Scale (SRDS; Smith & McVie, 2003)

Potential moderators
	
 1. Out of home placement 2. Learning disabilities (LD): Estimated Verbal IQ based on two subtest of the Wechsler Abbreviated Scale of Intelligence. 3. Ethnicity

Planned number of sites
	
6 local authorities across England

Inclusion criteria
	
Families of young people aged 11-15 years determined as being on the edge of care
 
Definition of Edge of Care
 
Edge of Care refers to children/young people who either:
 
 • have not entered into care as they have been assessed and the LA has chosen to support them and their families through alternative provisions/services. Or • they are being considered for care but have not entered into local authority care.

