Fidelity: The fidelity score is the average proportion of sessions content delivered. Fidelity items will be scored 0, 0.5, and 1. Total fidelity session score will be dependent on the session and will range between 20 and 30. This is based on agreed progression criteria and Triple P guidance on minimum number of sessions required in their opinion as the intervention developer.

Adherence: Number of sessions attended (Progression criteria: green= \geq 75% of families attend at least the first 8 of the 10 sessions; amber= 50-74%; red= $<$ 50%). The proportion of sessions attended out of a maximum of ten will be the instrumental variable in this analysis.

For both fidelity and adherence, a Two Stage Least Square approach will be used to estimate the model and Huber-White standard errors reported which are robust to clustering. The R packages ‘ivpack’ and ‘ivreg’ will be used to implement the two-stage instrumental variable analysis (Jiang & Small, 2014; Fox Kleiber, & Zeileis, 2021). Compliance (session adherence) will be instrumented by the intervention allocation (Angrist & Imbens, 1995). However, robust SE will be reported instead of including random effects in to the model. The stage 1 model is defined as follows:

$$Compliance_k = \beta_0 + \beta_1 TX_k + \varepsilon_{jk}$$

Predicted values for, $Compliance_k$, from the stage 1 model will be included in the stage 2 model, as follows:

$$Y_{ik} = \beta_0 + \beta_1 \widehat{compliance}_k + \beta_2 baseline_{ik} + \beta_3 Local_authority_k + \beta_4 \widehat{compliance}_k \cdot Local_authority_k + r_{ik}$$

Subgroup analyses

In addition to the primary and secondary outcomes, we have considered that the following outcomes may moderate the primary outcome of this trial.

- Ethnicity,
- In-care vs family home status: all instances of out of home placement will be recorded at each follow-up time point. This will include the reason for and duration of out of home placement.
- Learning disabilities (LD): Children and young people will be invited to complete two subtests of the Wechsler Abbreviated Scale of Intelligence-II (WASI-II; Wechsler, 2011) to index their Verbal IQ. This scale is to be administered with a researcher (face-to-face, telephone, videoconferencing). The two subsets are to be included are Vocabulary and Similarities.

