A moderation analysis will adjust the primary analysis with the inclusion of the moderator as a main effect and interaction between moderator and randomised group indicator. For example, the LD moderator analysis is as follows:

$$L1: Y_{ik} = \beta_{0k} + \beta_{1k} SDQ_BL_{ik} + \beta_{2k} local_authority_{ik} + \beta_{3k} LD_{ik} + r_{ik}, \quad r_{ik} \sim N(0, \sigma^2)$$

$$L2: \beta_{0k} = \gamma_{00} + \gamma_{02} TX_k + \mu_{0k}, \quad \mu_{0k} \sim N(0, \tau_2^2)$$

$$\beta_{1k} = \gamma_{10}$$

$$\beta_{2k} = \gamma_{20}$$

$$\beta_{3k} = \gamma_{30} + \gamma_{20}TX_k$$

where, Y_{ik} are the SDQ scores; SDQ_BL_{ik} are the baseline SDQ scores; TX_{ik} is the treatment/control variable indicator; $Local_authority_{ik}$ are indicator of local authority (strata); LD_{ik} is learning disability status; μ_{0k} is the random intercept term for family; and r_{ik} is the individual level variation.

In addition to interpreting the magnitude and statistical significance of interactions, plots of the interactions will also be examined. These analyses will be hypothesis generating in nature only (i.e., will not be confirmatory and only indicate whether further research targeting the intervention may be warranted).

Missing data

Exploring the impact of missing data on the primary trial outcome by investigating likely missing data mechanisms and re-fitting the primary outcome within a multiple imputation framework (including exploring MAR and MNAR mechanisms via delta-based controlled multiple imputation).

We will summarise the extent of missing data in all outcomes and their respective control variables. A full multiple imputation strategy will be used if more than 5% of data in the primary model is missing. Alternatively, we will impute if more than 10% of data for a single variable is missing. We will use the multiple imputation by chained equations approach via the mice package in R (Van Buuren and Groothuis-Oudshoorn, 2011) and generate 10 imputed datasets. We will then estimate the intervention effect for each imputed dataset and pool the results using Rubin's combination rules for standard errors.

Missing data in item level data

The sum scores will not be imputed directly. Any missing item level data will be imputed using the chained equation approach. Each item's imputation model will use other items and covariates specified in the primary analysis model as predictors.

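### The SAP defines the in-care moderator by placements recorded after randomisation, and contradicts itself on whether out-of-home placement is a tested secondary outcome

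*SAP*

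**What the plan says.** **As a moderator.** The SAP summary table lists "Out of home placement" first among the potential moderators. Its Subgroup analyses section says "we have considered that the following outcomes may moderate the primary outcome of this trial" and describes the in-care variable thus: "In-care vs family home status: all instances of out of home placement will be recorded at each follow-up time point". The moderator then enters the primary model through "inclusion of the moderator as a main effect and interaction between moderator and randomised group indicator". The section adds that "These analyses will be hypothesis generating in nature only". The protocol (Analysis of primary and secondary outcomes) already names in-care versus family home status as a moderator, without tying it to follow-up placements. Objective 3 in both documents frames the subgroup as foster versus biological or adoptive parents.

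**As an outcome.** Protocol secondary outcome 12 reads "all instances of out of home placement will be recorded at each follow-up time point". Objective 2(d), in both documents, asks whether the programme "reduces the chance of a child going into out of home placement over a 12 month period".

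**At entry.** One limb of the edge-of-care definition is "they are being considered for care but have not entered into local authority care", and the other limb likewise requires that the young person has not entered care. Both documents nevertheless recruit foster carers (Protocol, Design and Procedure; SAP, Trial design and Analysis population). The SAP schedules placement at baseline. Its List of baseline data also records whom the young person lives with and whether they are looked after.

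**The concern.** A moderator should be fixed before allocation. Here the only time points named are follow-ups, and the variable is one that treatment is meant to change. If the programme keeps some of the more severe adolescents at home, the home group in the intervention arm gains severe cases. The placed group in that arm is then left with the most severe. Both strata can look worse under intervention without any harm to behaviour, and the planned interaction plots would display exactly these stratum effects.

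Timing adds to the problem. The primary model analyses the SDQ at 6 months, while follow-up placements run to 12 months. Some would come after the outcome they are supposed to moderate, and might result from it.

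The second issue is the status of placement as an outcome. An analyst could report it inside the Holm family, outside it, or only as a moderator, and could cite some part of the SAP for each. Leaving that choice until the data are visible would make it data-dependent.

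**Working it through.** **1. Placement as an outcome in the SAP**

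| Present | Absent |
|---|---|
| Objective 2(d) | Summary-table secondary outcomes |
| Trial design table, outcome 12 | Holm list (Adjustment of multiplicity) |
| Timing of outcome assessment | List of secondary outcomes |
| Secondary outcomes analysis, as the named binary outcome for which a logistic mixed model will be considered | Order of testing |
| | Timing, units and derivation of secondaries |

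Placement therefore has an objective and a candidate model. It has no scoring rule, no analysis time point and no Holm slot.

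**2. The plan's own sample size, for scale.** Inputs (SAP, Sample size): d = 0.35, power 90%, two-sided 0.05, r = 0.5, ICC 0.5, 1.5 parents per family, 20% of families lost. A two-sample t-test needs 172.5, so 173 per arm. Then × (1 − 0.5²) = 129.75 → 130; × (1 + 0.5 × 0.5) = 162.5 → 163 parents; / 1.5 → 109 families; / 0.8 → 137 families; × 1.5 = 205.5 → 206 per arm, 412 in total. This reproduces, and nothing below changes it.

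**3. Illustrative upper bound.** The documents give no placement rate, so these are assumptions: no true SDQ effect; placement 30% in control and 20% in intervention; placement occurs exactly when standard normal severity Z exceeds a cut-off; no baseline adjustment. With q the p-quantile and φ the normal density, E[Z | Z < q] = −φ(q)/p and E[Z | Z > q] = φ(q)/(1 − p).

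- Control: p = 0.70, q = 0.524, φ = 0.3477. Home mean −0.497, placed mean 1.159.
- Intervention: p = 0.80, q = 0.842, φ = 0.2800. Home mean −0.350, placed mean 1.400.
- Spurious harm: home −0.350 + 0.497 = 0.147 SD; placed 1.400 − 1.159 = 0.241 SD; interaction 0.241 − 0.147 = 0.094 SD.
- Severity–outcome correlation 0.6: 0.09, 0.14 and 0.06 SD.

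**4. Softer versions at the same rates.**

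- Adjusting for a baseline SDQ correlated 0.5 with outcome, as the plan assumes, turns 0.15 and 0.24 into 0.13 and 0.21.
- If severity also correlates only 0.6 with both placement liability and outcome (assumed), they fall to 0.04 and 0.07, with 0.03 in the interaction.

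**5. Simulation with a true effect.** Set-up: 220 evaluable families (275 × 0.8), one record each; true effect −0.35 SD in everyone, with no moderation; baseline adjusted. Placement depends on baseline and on unmeasured severity, with log-odds slope 0.7 or 1.5 per SD of severity (all assumed).

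| Placement odds ratio | Slope | Placed, control / intervention | Effect, home | Effect, placed | Interaction bias (sampling SD) |
|---|---|---|---|---|---|
| 1 | 0.7 | 18% / 18% | −0.35 | −0.35 | 0.00 (0.31) |
| 1 | 1.5 | 23% / 23% | −0.35 | −0.34 | +0.01 (0.26) |
| 0.5 | 0.7 | 18% / 10% | −0.32 | −0.31 | +0.01 (0.35) |
| 0.5 | 1.5 | 23% / 15% | −0.30 | −0.27 | +0.03 (0.28) |
| 0.25 | 0.7 | 18% / 6% | −0.30 | −0.29 | +0.01 (0.44) |
| 0.25 | 1.5 | 23% / 9% | −0.26 | −0.19 | +0.07 (0.33) |

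A moderator unaffected by treatment, as a baseline one would be, gave −0.35 and −0.36, which is the true value within simulation error. The distortion sits in the stratum effects far more than in the interaction test.

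**6. Holm.** Counting each listed row as one test, the first step is 0.05/12 = 0.0042 now and 0.05/13 = 0.0038 with placement added.

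**The case against.** The sentence in the SAP's subgroup section is nearly the protocol's outcome text carried over. It says how placement is recorded and never states which value enters the interaction. A baseline record exists, so the intended moderator may be a baseline one that was poorly described. The analysis is labelled hypothesis generating, and the bias in the interaction is small beside its sampling error.

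Much of this stands. It limits the consequence, but it does not supply the missing definition. Follow-up is the only timing the subgroup section gives, the summary table names placement itself as the moderator, and nothing says that the baseline value is used. Calling an analysis exploratory does not make a confounded stratum estimate informative.

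A reader might also infer three stronger claims that the documents do not support:

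- **The SAP invented the moderator.** It did not: the protocol already names in-care status. What the SAP adds is the follow-up definition.
- **The moderator can only come from follow-up, because nobody is in care at entry.** Foster carers are recruited, the protocol provides for consent when the local authority holds parental responsibility, and looked-after status is recorded at baseline. The eligibility wording conflicts with these provisions. That is a contradiction to reconcile, not proof that the baseline category is empty.
- **Placement has been dropped as an outcome.** It survives in four places in the SAP.

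**Conclusion.** The point holds in two parts. First, followed as written, the in-care subgroup conditions on an outcome that arises after randomisation and that treatment is expected to change. Second, the SAP is inconsistent on placement as an outcome and leaves objective 2(d) without a definition, a time point or a multiplicity-controlled test.

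The bias exists only if treatment affects placement, and its size cannot be obtained from the documents. The 0.15 and 0.24 SD figures are an upper bound for one assumed pair of placement rates. They should not be read as the expected bias, nor set against the 0.35 SD target as though the primary estimate were at risk. Milder assumptions bring them down to 0.04 and 0.07 SD. The interaction bias was below 0.1 SD in every case tried.

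The primary analysis, its error rate and the sample size are unaffected. This should be corrected before any analysis by arm, but it does not threaten the main result.

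**What to change.** 1. In the SAP summary table and Subgroup analyses, remove follow-up placement from the moderators. Define the subgroup only from living arrangement recorded at baseline, as foster versus biological or adoptive parents, in line with objective 3.
2. Reconcile the edge-of-care eligibility wording with the inclusion of foster carers in both documents. If the baseline category then proves near-empty, drop this subgroup and say so.
3. Restore placement to the SAP's summary table, secondary-outcome list, derivations, order of testing and Holm family. Define it as any out-of-home placement by 12 months, with one record per adolescent (the protocol anticipates one responding adolescent per household). Analyse it by logistic regression on arm and local authority, and report it with the 12-month outcomes.

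**Cost.** Wording only. The schedule already collects both the baseline variable and the placement records, and 412 stands. The one statistical price is the slightly stricter first Holm step, 0.0038 instead of 0.0042.

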All participants (in both trial arms) will complete assessments at baseline (prior to randomisation), 6- and 12-months post-randomisation and will be given a choice of how these are completed. These assessments can be completed in a number of ways, face-to-face, online on a website, via telephone, via videoconferencing, or on paper via the post. Participants, parents/guardians, young people and key stakeholders will be invited to participate in semi-structured interviews to ascertain acceptability and their experience of

the parenting programme and being in the trial. We will interview a sample of those randomised to each arm of the trial.

Randomisation

Families will be randomised with equal probability to either the intervention or comparator arm using random permuted blocks (block size 4), stratified by local authority site. The statistician doing the analysis will be blind to the treatment allocation. As the families and practitioners are not blind to treatment allocation (as this would be impossible given the intervention), there is no issue in terms of predictability.

Sample size

Sample size calculations were conducted using R version 4.1.2 (2021-11-01), and the 'pwr' R package.

Parents/carers within the same family will be randomised to the same arm, making this a cluster RCT, given responses within the same family are potentially highly correlated. We might expect, based on our previous research with families and consultation with the TMG (Trial Management Group), an average cluster size within families of up to a maximum of 1.5 parents and a high degree of correlation among parents/carers from the same family, so also allow for an ICC=0.5 (Davé et al., 2008). Following Teerenstra et al. (2012), we also allow for a correlation between baseline and follow-up measures of primary outcome of $r=0.5$ (this is a conservative estimate based on published SDQ test-retest correlations between 0.74-0.84; Nowak et al., 2008). The sample size is then inflated to account for 20% of families being lost to follow-up at the 12-month post-randomisation follow-up time point.

Allowing for the above assumptions and an effect size to be detected of 0.35 with 90% power and a two-sided alpha of 0.05, a sample size of $N=412$ ($N_1=206$, $N_2=206$) is required.

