Baseline and 6-month follow up data will only be used in the primary analysis. The 12 month follow up data will be used both in the addendum primary analysis and in an additional follow up analysis including all three time points in a linear mixed model (see section 6.4 – longitudinal follow up analyses). The SDQ consists of 25 items which are each scored on a 3-point Likert scale (0, 1, 2). Externalising scores - Ranges from 0-20 and is generated by summing the scores of the conduct and hyperactivity subscales.

List of secondary outcomes

Secondary outcome measures include:

- Emotional and behavioural difficulties and prosocial behaviour: the Parent report and adolescent self-report versions of the Strengths and Difficulties Questionnaire (SDQ) will be used (including internalising, externalising, peer relationship, and prosocial behaviours). The SDQ is a robust and well-validated measure of behavioural and emotional problems (Deighton et al., 2014); measured over the preceding 6 months.
- Parenting practices: Parenting Scale Adolescent version (PSA, parent completed) is a short form of the Parenting Scale (Irvine et al., 1999) which assesses dysfunctional discipline practices in parents. It is an adaptation of the Parenting Scale (Arnold, et al., 1993) for parents of adolescents
- Interparental outcome - Dyadic Adjustment Scale (DAS-7) is a 7-item measure (Sharpley & Cross 182; Hunsley et al., 2001) assessing the relationship quality of couples. The DAS-7 assesses relationship satisfaction and the degree to which the couple agrees on matters of importance to the relationship.
- Parent mental health – the Kessler Psychological Distress Scale (Kessler 6) is a six-item screening tool for serious mental illness in the general population (Kessler et al., 2003). It will be completed by parents.
- Parent Wellbeing - The Warwick-Edinburgh Mental Well-being Scale (SWEMWBS) is a measure of mental wellbeing (Tennant et al., 2007). The short (7 item) version will be completed by parents.
- Conflict Behavior Questionnaire (CBQ-20) (Robin & Foster, 1989) assesses adolescent-parent communication, conflict and relations. Both the adolescent and parent report versions will be completed.
- Child-parent relationship – the Closeness subscale of the Child-Parent Relationship Scale (CPRS, short form) measures (Pianta, 1995) will be completed by parents.

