Following creation of the imputed datasets, the corresponding total scores will be calculated using the imputed item level data. All imputed datasets will then fit the primary and secondary models and pool estimates following Rubin's rules (Rubin, 2004; van Buuren, 2018).

Primary outcome

Given that each item is an ordered category, we will use an ordinal regression within the imputation model for each item.

Secondary outcome Similarly, the correct link function will be used according to the item's structure for each of the secondary outcomes, i.e. binary or ordered categorical accordingly. Therefore, a logistic or ordinal model will be used in the imputation for these items.

Additional analyses

Longitudinal followup analyses (12 month only) – Primary outcome

We will fit linear mixed models, accounting for repeated post-randomisation measures (6- and 12-months post-randomisation) within participants, adjusting for local authority to investigate the overall effect of the intervention on post-randomisation measures.

$$L1: Y_{ijk} = \beta_{0jk} + \beta_{1jk}time_{ijk} + r_{ijk}, \quad r_{ijk} \sim N(0, \sigma^2_{|X})$$

$$L2: \beta_{0jk} = \gamma_{00k} + \mu_{0jk}, \quad \mu_{0jk} \sim N(0, \tau_2^2)$$

$$\beta_{1jk} = \gamma_{100} + \mu_{1jk}, \quad \mu_{1jk} \sim N(0, \tau_2^2)$$

$$L3: \gamma_{00k} = \delta_{000} + \delta_{001}local_authority_k + \delta_{001}TX_k + \varsigma_{0k}, \quad \varsigma_{0k} \sim N(0, \tau_3^2)$$

Longitudinal followup analyses (12 month only) - Secondary outcomes

Secondary outcomes will be analysed similarly, but

$$L1: g(Y_{ijk}) = \beta_{0jk} + \beta_{1jk}time_{ijk} + r_{ijk}, \quad r_{ijk} \sim N(0, \sigma^2_{|X})$$

$$L2: \beta_{0jk} = \gamma_{00k} + \mu_{0jk}, \quad \mu_{0jk} \sim N(0, \tau_2^2)$$

$$\beta_{1jk} = \gamma_{100} + \mu_{1jk}, \quad \mu_{1jk} \sim N(0, \tau_2^2)$$

$$L3: \gamma_{00k} = \delta_{000} + \delta_{001}local_authority_k + \delta_{001}TX_k + \varsigma_{0k}, \quad \varsigma_{0k} \sim N(0, \tau_3^2)$$

For the remaining secondary outcomes, their effect sizes will be reported as either Hedges' g (same as primary outcome) or rate ratios (other secondary outcomes, exponentiated parameter estimates), given that generalized linear mixed effects models with log link function are used to model the data and that the measures are positively scored integers with some amount of skew anticipated (Barnett and Dobson, 2008).

Mediation analyses (12 months report only)

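### DAS-7 is scheduled for every parent with no partner requirement, so the SAP's item imputation rule, applied as written, would give couple scores to parents without a partner

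*SAP*

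**What the plan says.** **The measure.** The SAP's List of secondary outcomes describes the DAS-7 as "assessing the relationship quality of couples". The derivation section sums seven items to a 0 to 36 score and gives no not-applicable rule. The SAP's Trial design has all participants complete the assessments, and its timing table places DAS-7 at baseline, 6 and 12 months.

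**Who is in the trial.** The eligibility criteria in both documents do not require a parent to have a partner. A second parent joins only by choice (SAP, Trial design). The Sample size section expects "an average cluster size within families of up to a maximum of 1.5 parents".

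**Missing data.** The SAP starts imputation when more than 5% of the data in the primary model, or more than 10% of one variable, is missing. Under Missing data in item level data it then says "Any missing item level data will be imputed using the chained equation approach", followed by "All imputed datasets will then fit the primary and secondary models and pool estimates following Rubin's rules". A further paragraph gives the imputation model types for secondary-outcome items. DAS-7 is not exempted.

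**Analysis.** The SAP's primary analysis uses participants who provide outcome data, and secondary outcomes follow the same method. The interparental outcome is fifth of the 12 listed under the Holm procedure.

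**The concern.** A parent with no partner has no couple relationship to rate. Blank DAS-7 items from such a parent are structurally undefined; there is no unseen true value for an imputation model to recover. Neither document separates these cells from ordinary non-response, so the item rule covers both.

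At stake is the meaning of the interparental result, which serves secondary objective 2(c). An analysis of the imputed datasets would describe a population that includes people for whom the outcome does not exist, and its N would exceed the number of parents able to supply a score. Because the observed and imputed analyses cover different populations, it also matters which of them is the formal test, and the SAP leaves that open.

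**Working it through.** **1. The plan's own sample size.** Inputs, all from the SAP's Sample size section: "an effect size to be detected of 0.35 with 90% power and a two-sided alpha of 0.05"; "we also allow for a correlation between baseline and follow-up measures of primary outcome of" 0.5; "so also allow for an ICC=0.5"; mean cluster size 1.5; "The sample size is then inflated to account for 20% of families being lost to follow-up".

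- Unadjusted n per arm for d = 0.35: 172 (normal approximation) or 173 (t test).
- Design effect: 1 + (1.5 − 1) × 0.5 = 1.25. Baseline-adjustment factor: 1 − 0.5² = 0.75.
- 172 × 1.25 × 0.75 / 0.8 = 201.6 per arm, total 404. With 173: 202.7 per arm, total 406.

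The stated 412 is within 2% of these, so it is reproduced. 412 / 1.5 = 274.7, hence 275 families. Neither document gives a sample size or a number of partnered parents for DAS-7.

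**2. How many parents could be affected.** Assumption: each family has one or two respondents, and two respondents are a couple. Then 412 − 275 = 137 families have two respondents and 275 − 137 = 138 have one. The share of sole respondents without a partner (s) is not stated, so a range is shown. Number not applicable = 138 × s.

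**3. Size and power if DAS-7 is restricted to partnered parents.** Loss of 20%; d = 0.35, r = 0.5 and ICC 0.5 borrowed from the primary outcome; design effect recalculated for the remaining mean cluster size. Example at s = 1: parents 0.8 × (412 − 138) = 219; families 0.8 × (275 − 138) = 109.6; mean size 2.0; design effect 1.5.

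| s | Not applicable, of 412 | Partnered parents analysed | Power, alpha 0.05 | Power, alpha 0.05/12 |
|---|---|---|---|---|
| 0 | 0 | 330 | 0.91 | 0.66 |
| 25% | 34 (8%) | 302 | 0.87 | 0.59 |
| 50% | 69 (17%) | 274 | 0.83 | 0.51 |
| 75% | 104 (25%) | 247 | 0.76 | 0.43 |
| 100% | 138 (33%) | 219 | 0.69 | 0.34 |

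The last column is the strictest Holm step for 12 outcomes.

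**4. Would imputation be triggered?** The planned 20% loss exceeds both limits, but it is a 12-month figure and the SAP gives none for 6 months. Structural gaps alone pass the 10% limit for DAS-7 once 42 of 412 parents have no partner (0.10 × 412 = 41.2), which is 42/138, about 30% of sole respondents.

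**5. Effect on the estimate.** A simplified simulation used a total score, 330 parents, r = 0.5, a true effect of 0.35, 10 imputations, 400 runs and no family clustering. Each cell gives partnered-only, then imputed.

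| Not applicable | Arm in imputation model: estimate | Power | Arm left out: estimate | Power |
|---|---|---|---|---|
| 10% | 0.352, 0.351 | 0.94, 0.95 | 0.346, 0.311 | 0.94, 0.91 |
| 20% | 0.352, 0.352 | 0.91, 0.92 | 0.351, 0.280 | 0.92, 0.80 |
| 33.5% | 0.344, 0.345 | 0.82, 0.80 | 0.353, 0.234 | 0.85, 0.57 |

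With arm included, imputation neither biases the estimate nor adds real precision: the extra rows carry no information. With arm left out, the estimate shrinks towards zero. The SAP's predictors are the other items and the primary model's covariates. That model contains the arm indicator, so inclusion is plausible, but it is not explicit.

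**The case against.** The strongest reply is that the SAP already has an analysis free of the problem. Secondary outcomes follow the primary method, which uses people who supply outcome data, so a parent with no DAS-7 score simply drops out. The Sensitivity analyses section and the opening of Missing data frame imputation around the primary outcome. The item rule, which predicts each item from other items, may have been written for partly completed scales. The questionnaires are not among the documents and may contain a skip option. The SAP also promises to summarise missing data for every outcome, so the observed DAS-7 count should be visible.

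Much of this stands. A reader might infer that the Holm-tested interparental result will certainly rest on imputed scores for lone parents. The documents do not support that, because they do not say which version is tested. A reader might also infer that couples who separate will be filled in from intact couples. No passage says how a separated parent answers or is coded. Nor can the plan be said to present a small couples sample as the full one, given the promised missing-data summary.

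The reply does not remove the rule itself. The text sends imputed datasets into the secondary models and names imputation models for their items, with no exemption for DAS-7. The observed-data route needs a rule too: without one, it is unclear whether a parent without a partner skips the scale or answers about a former partner.

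**Conclusion.** The point holds conditionally. If the item-level rule and the instruction to fit secondary models to the imputed datasets are applied as written, parents without a partner receive DAS-7 totals. The imputed interparental analysis then covers people for whom the outcome is undefined and overstates the number of parents it rests on.

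The extent cannot be fixed from the documents. The 8% to 33% range depends on equating two respondents with a couple and on an assumed share of unpartnered sole respondents. One respondent does not mean one parent, and two respondents need not be a couple. It would be tempting to claim a biased treatment effect; the simulation supports that only if arm is left out of the imputation model, which the SAP does not state. The main faults are therefore the undefined population and the inflated N. The observed-data DAS-7 analysis and the primary outcome are unaffected.

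**What to change.** In the SAP and the parent questionnaire:

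- Add one yes/no item on having a partner, for each responding parent at each time point. The household variable in the SAP's baseline list records who the young person lives with, and the parent list has no partner item. Household data also miss a partner who lives elsewhere.
- Define the DAS-7 analysis set as parents with a partner at baseline. This status is fixed before randomisation, so arm cannot influence it.
- Code DAS-7 as not applicable for other parents and exclude those cells from the mice run.
- State how a separation after baseline is handled in the analysis, and report separations by arm.
- Name arm explicitly as an imputation predictor.
- State whether the observed or the imputed DAS-7 result enters Holm, and report the actual N.

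The cost is some SAP wording and one short item. The DAS-7 sample becomes smaller and its power lower: under the borrowed assumptions, from 0.91 to between 0.87 and 0.69 at alpha 0.05 as s goes from 25% to 100%. No other outcome's sample is reduced.
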